7.1.7.2 Other safety endpoints

- (1) Rate of device-related AEs

Evaluation time: During the trial

Definition of device-related AE: refers to AE that is determined by the investigator to be related, possibly related, unlikely related to the device or the correlation between AE and device is unable to be judge. However, normal postoperative stress reactions, such as fever and constipation, should be distinguished, and those judged by investigators as normal postoperative stress reactions do not need to be recorded in adverse events.

- (2) Rate of SAEs

Evaluation time: During the trial

Serious adverse events refer to events that cause death or serious deterioration of health, including fatal

diseases or injuries, permanent defects of body structure or body functions, hospitalization or prolonged hospital stay, and medical or surgical intervention to avoid causing permanent defects to the body structure or body functions; or that cause fetal distress, fetal death or congenital abnormalities, congenital defects, in the process of the clinical study.

7.1.8 Device deficiency and corresponding evaluation, recording and analyzing method and time:

[figure not shown]
Rate of device deficiencies

Evaluation time: During the operation

Definition of device deficiency: refers to the deficiency of the investigational device which presents in the trial process, such as label error, plastic thread damage, ineffective fastening or release of the locking piece, displacement of shunt blocking membrane, etc.

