13.1 Definition of adverse event

AE refers to adverse medical events occurs during clinical trials, whether related to the test medical devices or not. The possible AEs in this study include: (1) common complications; (2) Expected or unexpected SAE; (3) Expected or unexpected AE

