13.1.2 Report and handling of AEs

All AEs observed during the trial must be truthfully recorded in the adverse event form. Investigator should carry out targeted treatment and follow-up to AEs until symptoms disappear or become stable.

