13.1.4.3 Expected and unexpected AEs and corresponding treatments

- (1) Transient arrhythmia: It is usually diagnosed by ECG, which is mostly transient during operation without special treatment;
- (2) Fever: It can be judged by clinical examination. The investigators usually need to analyze the cause of fever and treat it symptomatically;
- (3) Other unexpected AEs

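### Protocol 7.1.7.2 exempts undefined normal postoperative stress reactions from AE recording, in conflict with Protocol section 13 and SAP 6.1, so the descriptive AE rates can be undercounted by an unknown amount

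*Protocol*

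**What the plan says.** Protocol 7.1.7.2 defines a device-related AE broadly: it "refers to AE that is determined by the investigator to be related, possibly related, unlikely related to the device", and it also includes events whose relation cannot be judged. The same paragraph then adds that "normal postoperative stress reactions, such as fever and constipation, should be distinguished", and that those "judged by investigators as normal postoperative stress reactions do not need to be recorded in adverse events".

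Protocol section 13 has no such exception:
- 13.1: "AE refers to adverse medical events occurs during clinical trials, whether related to the test medical devices or not".
- 13.1.2: "All AEs observed during the trial must be truthfully recorded in the adverse event form".
- 13.1.4.3, the list of expected and unexpected AEs: "Fever: It can be judged by clinical examination. The investigators usually need to analyze the cause of fever and treat it symptomatically".

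Protocol 7.3, item 6, asks monitors to confirm that all AEs have been recorded. SAP 3.2.3 names the incidence of device-related AEs as an endpoint. SAP 6.1 tabulates all treatment-emergent AEs, intraoperative and postoperative, together with device-related and procedure-related AEs, and does not mention the exception. SAP 6.1.1 counts an event of unclear relationship as related.

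**The concern.** The exception acts on recording, not on attribution. A fever that is entered as an AE passes through the causality field and, if the relation is unclear, is counted as related. The same fever called normal stress has no AE entry and reaches no AE table. Two sites could handle the same fever differently and each cite the protocol.

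At stake are the device-related AE rate, which is a named safety endpoint, and the treatment-emergent and procedure-related AE tables. Protocol 8.2.1 describes the device as a first clinical use of an absorbable material for this purpose, and Protocol section 4 reports a lower inflammatory reaction than the metal comparator in animals. A reader of the report would take the AE tables to be complete on events such as fever.

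**Working it through.** The plan gives no expected AE or fever rate and no AE threshold, so there is no figure of its own to reproduce. The check sets the passages side by side, followed by an illustration of size.

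**1. The same event under each section.** Take a fever two days after implantation that the investigator regards as ordinary.

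| Place | Treatment of the event |
|---|---|
| Protocol 13.1, 13.1.2 | An AE regardless of relation; must be recorded |
| Protocol 13.1.4.3 | Fever listed by name as an AE |
| SAP 6.1 | Postoperative event, tabulated |
| Protocol 7.1.7.2 | Need not be recorded |

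**2. What limits the exception.** Protocol 7.1.7.2 gives no temperature, duration, time window or grade. It requires no log and no independent review, and it does not say that the SAE criteria in 13.2 override it. Recording mild events is already workable: Grade 1 in 13.1.1 covers mild events that need no intervention.

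**3. Direction.** Compared with recording everything, the exception can only remove events. The rule in SAP 6.1.1 for unclear relationship cannot act on an event that was never entered.

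**4. What it reaches.**
- The primary safety endpoint (Protocol 7.1.7.1, SAP 3.2.1) is seven named complications. Fever and constipation are not among them, so that endpoint, its comparison with 6% and the sample size do not change.
- The SAE rate changes only if an event that meets an SAE criterion, such as a prolonged hospital stay, is first judged normal stress.
- The device-related AE rate and the AE tables do change. SAP section 6 makes these descriptive, with no test.

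**5. What else would show the event.** Body temperature is a vital sign (Protocol 7.2.3.1). The schedule in 7.2.2 has vital signs before operation, before discharge and at each later visit, with none in between, so a fever that settles before discharge can be missed. The CRF medication record covers only anticoagulants, antiplatelets and antibiotics, so other treatments for fever or constipation leave no trace there. No scheduled item captures constipation.

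**6. Illustration of size (assumptions, not document figures).** Let N = 146 planned subjects, b = 15% with some other recorded AE, f = the share with postoperative fever or constipation (independent of b), and d = the share of those reactions exempted.

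- Any-AE rate if all are recorded: 1 − (1 − b)(1 − f)
- Any-AE rate under the exception: 1 − (1 − b)(1 − f(1 − d))
- Subjects lost from the count: N(1 − b)fd

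| f | All recorded | d = 1: rate; subjects lost | d = 0.5: rate; subjects lost |
|---|---|---|---|
| 5% | 19.3% | 15.0%; 6.2 | 17.1%; 3.1 |
| 10% | 23.5% | 15.0%; 12.4 | 19.3%; 6.2 |
| 20% | 32.0% | 15.0%; 24.8 | 23.5%; 12.4 |
| 30% | 40.5% | 15.0%; 37.2 | 27.8%; 18.6 |

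For example, f = 30% and d = 1 gives 146 × 0.85 × 0.30 = 37.2. SAP 3.1 plans 142 subjects rather than 146; with 142 the same cell is 36.2.

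**The case against.** The best defence is that the sections can be read together. A reaction that is normal after surgery may fall below the threshold of an adverse medical event, in which case 13.1.2 is not breached. Section 13.1.4.3 expects the cause of a fever to be analysed, which fits with separating normal from abnormal fever, and fever with another cause remains an AE. This shows that the conflict could be resolved by interpretation. It does not resolve it, because nothing in the documents says where normal ends and section 13 does not refer to the exception.

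A reader might infer that the judgement cannot be reviewed or reversed. The documents do not support that. Temperature is recorded at scheduled visits and vital signs are analysed (SAP 3.2.3 and section 6). White cell count and neutrophil percentage are repeated before discharge, antibiotics are on the CRF, monitors check original data (Protocol 7.3, 11.2.2 and section 16), and entries can be queried before lock (9.3, 9.4). This cover is real but partial, for the reasons in step 5 of the working. In addition, a monitor who finds an unrecorded fever in the source cannot clearly call it an error while 7.1.7.2 stands.

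It is also fair to say that the exception concerns postoperative reactions and does not on its face cover a late fever, and that the affected analyses are descriptive. Both points limit the consequence and both stand.

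**Conclusion.** The concern holds as a conflict over event recording. Protocol 7.1.7.2 contains an undefined exception that Protocol 13.1, 13.1.2 and 13.1.4.3 and SAP 6.1 do not share. The device-related AE rate and the treatment-emergent and procedure-related AE tables can be undercounted, in one direction, by an unknown amount that may differ by site.

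Three stronger conclusions are tempting and go too far:
- That AEs are in fact undercounted. The documents show only that they can be.
- That trial success is affected. The primary safety endpoint, its test against the OPC and the sample size are untouched, and the SAE rate is exposed only in the case described in step 4.
- That a definite number of subjects is missing. Applying a 5% to 20% fever rate to 146 gives 7.3 to 29.2, but that rate is an assumption. The product also supposes that every such fever is exempted and that none of those subjects has another recorded AE. The table in the working depends on its assumptions in the same way.

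The passages should be reconciled. The point does not threaten the primary conclusion.

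**What to change.** Remove the recording exception from Protocol 7.1.7.2. Record every event under 13.1.2, add a CRF flag for a normal postoperative stress reaction, and have SAP section 6 present the AE tables with and without flagged events. The investigator's judgement is then kept, but it is visible and can be reviewed. The cost is a wording change, one CRF field, a few more AE entries and a higher raw AE rate.

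A weaker alternative is to keep the exclusion but define it objectively, state how it relates to the SAE criteria, and repeat it in Protocol section 13 and in the SAP.

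If the data are already collected, the report should disclose the exception next to the AE tables and list recorded temperatures by visit. That gives a partial check on fever and none on constipation.

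The same edit should settle a related mismatch: Protocol 7.1.7.2 counts unlikely-related events as device-related, while SAP 6.1.1 groups them as unrelated.

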7.2 Trial process

7.2.1 Trial Flowchart

7.2.2 Data collecting summary

Number of visits Visit item	Screening stage	Enrollment stage									
	Before operation	Intraoperative	Visit 1	Visit 2	Visit 3	Visit 4	Visit 5	Visit 6	Visit 7	Visit 8	Visit 9
Observation cycle	-30~0d	0d	Before discharge	30±7d	90±14d	180±30d	360±30d	2y±60d	3y±60d	4y±60d	5y±60d
Informed consent form	▲										
Demographic data	▲										
Vital signs	▲		▲	▲	▲	▲	▲	▲	▲	▲	▲
Current medical history	▲										
Past history	▲										
Inclusion/exclusion criteria	▲										
Pregnancy test	▲										
Urine routine	▲										
Blood routine	▲		▲		▲	▲	▲	▲	▲		
Liver function	▲				▲	▲	▲	▲	▲		
Kidney function	▲				▲	▲	▲	▲	▲		
Cardiac enzymes	▲		▲		▲	▲	▲	▲	▲		
Coagulation function	▲										
TTE	▲	▲	▲	▲	▲	▲	▲	▲	▲	▲	▲
Chest X-ray	▲					▲	▲				
ECG	▲		▲	▲	▲	▲	▲	▲	▲	▲	▲
Medication record	▲	▲	▲	▲	▲	▲					

Common complications			▲	▲	▲	▲	▲				
AE			▲	▲	▲	▲	▲	▲	▲	▲	▲
Device deficiencies		▲									

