13.2.1 Treatment of serious adverse events

- (1) If serious adverse events occur in the clinical trial, the investigator shall immediately take appropriate treatment measures, and meanwhile provide a written report to the medical device clinical trial management department of the clinical trial institution to which it belongs and notify the sponsor in writing;

- (2) The medical device clinical trial management department shall provide a written report within 24 hours to the corresponding ethics committee, the food and drug regulatory authority and the health and family planning department of the province, autonomous region or municipality where the clinical trial institution is located;
- (3) In case of deaths, the clinical trial institution and the investigator shall submit all necessary information to the ethics committee and the sponsor;
- (4) For SAEs and device deficiencies that may lead to SAEs, the sponsor should report to the drug regulatory agencies and the health and family planning department at the same level within 5 working days after being informed. The sponsor should also notify other clinical trial institutions and investigators participating in the trial, and notify the ethics committees of the clinical trial institutions in time through their medical device clinical trial management departments.

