13.3 Device deficiencies

13.3.1 Definition of device deficiency

Device deficiency refers to unreasonable risks of medical devices that may endanger human health and life safety under normal use conditions in the process of the clinical trial, such as label errors, quality problems, malfunctions.

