13.3.2 Possible device deficiencies in this trial

- (1) Possible device deficiencies include label error, plastic thread damage, ineffective fastening or releasing of locking pieces, displacement of shunt blocking membrane, etc.
- (2) Device deficiencies are recorded in the device defect record sheet, and device defects that may lead to serious adverse events will be reported and recorded within 5 working days.
- (3) If there are device deficiencies before operation, such as label error, plastic thread damage, ineffective fastening or releasing of locking piece, displacement of shunt blocking membrane, it is necessary to change a new absorbable ASD closure system for operation. In case of device deficiencies such as ineffective fastening or releasing of the locking piece during operation, multi-angle adjustment or pulling can be tried, and if necessary, the device can be reclaimed or taken out with the catcher.

14. Device management

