22.16 Inspector: refers to the personnel selected by the regulatory authorities to inspect the clinical trial of medical devices.

22.17 Deviation: refers to the situation of intentionally or unintentionally failing to comply with the requirements of clinical trial protocol.

22.18 Case report form: refers to the document designed according to the clinical trial protocol to record all the information and data of each subject obtained during the trial.

22.19 Endpoint: refers to the index used to evaluate the hypothesis of clinical trials.

22.20 Source data: refers to the original records of clinical findings, observations and other activities in clinical trials and all information in their approved copies, which can be used for reconstruction and evaluation of clinical trials.

22.21 Source file: refers to printed files, visual files or electronic files containing source data.

22.22 AE: refers to adverse medical events occur during clinical trials, whether related to the investigational device or not.

22.23 SAE: refers to the death or serious aggravation of health during clinical trial, including fatal diseases or injuries, permanent defects in body structure or body function, hospitalization or prolonged hospitalization, and medical or surgical intervention required to avoid permanent defects in body structure or body function, fetal distress, fetal death, congenital abnormality and congenital defect.

22.24 Device defect: refers to unreasonable risk that may endanger human health and life safety under normal use conditions during the clinical trial, such as label error, quality problem, malfunction, etc.

22.25 Standard operating procedure: refers to the standards and detailed written procedures drawn up for effectively implementing and completing each step in clinical trial.

22.26 Clinical data: refers to the safety and performance information obtained from relevant literatures or clinical use of medical devices.

23. List of participating personnel

Clinical trial personnel	Position	Title	Department

Investigator Statement

I agree:

1. Carry out the clinical trial in strict accordance with the Helsinki Declaration, the current Chinese regulations and the requirements of this trial protocol.
2. Record all required data accurately in the CRF, and complete the clinical trial report on time.

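### The device-deficiency rate is evaluated only during the operation, while the protocol defines deficiencies over the whole trial and foresees them before the operation

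*Protocol*

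**What the plan says.** Protocol section 7.1.8 introduces a rate of device deficiencies and gives its timing as "Evaluation time: During the operation". Its next sentence says that a deficiency "refers to the deficiency of the investigational device which presents in the trial process", which has no restriction to the operation. For the device-related AE and SAE rates just above it, 7.1.7.2 gives "Evaluation time: During the trial".

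The schedule in 7.2.2 follows the narrow window. The row "Device deficiencies" has a single mark, under the intraoperative column at day 0. None of the item lists in 7.2.4, preoperative or Visits 1 to 9, includes it.

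Three other places take a wider view:

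- 13.3.1 covers events "in the process of the clinical trial, such as label errors, quality problems, malfunctions".
- 22.24 covers risks arising "under normal use conditions during the clinical trial, such as label error, quality problem, malfunction".
- 13.3.2(3) begins "If there are device deficiencies before operation, such as label error, plastic thread damage" and calls for a replacement unit in that case. It then deals separately with faults during the operation.

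On recording and reporting, 13.3.2(2) sends deficiencies to a device defect record sheet with no time limit, and 7.3(6) has the monitor confirm that device defects are recorded. Section 13.2.1(4) states: "For SAEs and device deficiencies that may lead to SAEs, the sponsor should report", within five working days of being informed.

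**The concern.** A rate needs a numerator that matches its definition. Here the definition runs over the trial and the window over the operation, so a site or programmer who follows 7.1.8 and 7.2.2 as written will not count events that the definition says are deficiencies.

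Both ends are affected. Before the operation, the faults that 13.3.2(3) foresees (labelling, thread, locking piece, membrane) are the same examples that 7.1.8 uses to define a deficiency. After the operation, subjects attend nine visits over five years, and section 5.1 says that the PLLA degrades gradually after implantation. No visit asks whether the device has shown a deficiency.

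The 360-day report supports the registration application. If it gives a deficiency rate, a reader guided by the definition would take it to cover the trial, when it describes the procedure only.

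**Working it through.** No figure for this rate is stated, so there is nothing to reproduce. The check sets the passages side by side and counts the schedule marks.

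**1. Period covered in each place**

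| Place in the protocol | Period |
|---|---|
| 7.1.8, evaluation time | Operation |
| 7.2.2, schedule row | Day 0, intraoperative |
| 7.1.8, definition | Whole trial process |
| 13.3.1, definition | Whole trial |
| 22.24, definition | Whole trial |
| 13.3.2(3), handling | Before and during the operation |
| 13.3.2(2) and 7.3(6), recording | No time limit stated |

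The two entries that govern the rate are narrow. The three definitions are all wide. The contradiction sits inside 7.1.8 and does not depend on comparing distant sections.

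**2. Schedule count.** The table in 7.2.2 has 11 columns: screening, intraoperative and Visits 1 to 9. Device deficiencies are marked in 1 of 11. AEs are marked at 9 of the 9 post-operative visits, and TTE in all 11 columns. The narrow collection of deficiencies therefore agrees with the evaluation time and does not look like a stray phrase.

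**3. Where a deficiency falls, by time of discovery**

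- *Before the operation:* a deficiency by definition, outside the window if read literally. One ambiguity remains. In 7.1.4 the package is opened at step 2, after the sheath is introduced at step 1, so a fault found on unpacking could be called intraoperative. Section 13.3.2(3) nevertheless classes faults of this kind as before operation, and two sites could code the same fault differently.
- *During the operation:* inside both definition and window.
- *Visits 1 to 9:* a deficiency by definition, outside the window, and not prompted at any visit. It can be entered on the defect record sheet, but nothing says that the sheet feeds the rate.

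**4. Analysis.** Protocol 8.7.4 describes no analysis of this rate. SAP 3.2.3 lists device-related AEs, SAEs, laboratory tests, ECG, imaging and vital signs, but not device deficiencies. The SAP text reviewed ends at 6.1.1 and has no such analysis up to there. The denominator (devices or subjects) is not given in 7.1.8, 8.7.4 or that SAP text.

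**5. Scale.** Planned enrolment is 146 in the protocol and 142 in the SAP. One subject with an uncounted deficiency changes a per-subject rate by 1/146 = 0.68% or 1/142 = 0.70%, about 0.7 percentage points. This is a unit of scale only; the documents give no expected number of deficiencies.

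**The case against.** The strongest reply is that recording and reporting are handled outside 7.1.8, and this largely stands. The defect record sheet has no time limit, the monitor checks that device defects are recorded, and the five-working-day duty runs from when the sponsor is informed. AEs are collected to five years, and the SAP lists imaging among the other safety endpoints.

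Several stronger readings are tempting, and the documents do not support them:

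- *That deficiencies outside the operation cannot be recorded or will go unreported.* The recording and reporting sections do not depend on the 7.1.8 window. What is missing is a prompt at visits and a count in the rate.
- *That a fault found at, say, day 90 is not a deficiency because of its timing.* All three definitions cover it; it is only outside the window for the rate.
- *That the rate is zero by construction outside the operation.* It is not measured there, which differs from being reported as zero.
- *That exchanged units are certainly uncounted.* Some unpacking faults may be entered as intraoperative.
- *That locking-piece or membrane faults would show on follow-up TTE or X-ray.* Nothing in the documents says so. Section 13.3.2(3) places locking-piece faults before or during the operation and membrane displacement before it, and in 7.1.4 fastening precedes release.

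It is also fair to say that the rate is not a primary, secondary or SAP-listed endpoint. That limits the consequence but does not resolve the contradiction.

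**Conclusion.** The inconsistency is real and can be read directly from the text: the window in 7.1.8 and the mark in 7.2.2 are narrower than the definitions in 7.1.8, 13.3.1 and 22.24, and narrower than the situations foreseen in 13.3.2(3). Following the plan literally gives a rate that omits deficiencies found at Visits 1 to 9 and at least some of those found before the operation.

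The effect is small. The events are uncounted and unprompted, not lost. How many there would be is unknown. The two co-primary conclusions, the significance level, the power and the sample size do not depend on this rate.

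The conclusion assumes that the stated evaluation time governs what enters the rate. If the intention was always to count every entry on the defect record sheet, the protocol needs to say so, and the same edits are needed.

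**What to change.** 1. In 7.1.8, change the evaluation time to the whole trial, from receipt of the device at the site to the end of follow-up. Starting at receipt and not at package opening keeps label errors that are seen before the package is opened.
2. In 7.2.2 and in the lists for Visits 1 to 9 (7.2.4.2 to 7.2.4.10), add a yes/no device-deficiency item. State with it that intended resorption of the PLLA is not a deficiency; otherwise normal degradation could be recorded as a fault.
3. In 8.7.4 and the SAP, state that the rate is computed from all entries on the device defect record sheet. Show before-use deficiencies per device, including exchanged units, separately from intraoperative and post-implant deficiencies per subject. The quantities and serial numbers kept under 14.1 can supply the per-device denominator.

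The cost is one eCRF item at existing visits and one extra table, with no new examination. The reported rate may become slightly less favourable.
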